10.1.2 Safety and Feasibility Endpoints

Safety Analysis: Our DSMB will examine all grade II or higher AEs and all SAEs in CN-105 and placebo treated patients. The expected rate of moderate and severe adverse events in this patient population is 5% each, based on historical Duke orthopedic surgery data; thus we expect similar AE rates in this trial in placebo- treated patients. At the end of each 67 patient randomized group, the DSMB will examine grade II or higher AE rates in drug-treated vs placebo-treated patients, and consider whether the study should be stopped or whether other corrective action should take place. An independent statistician will prepare summary reports (including all grade II or higher AE rates in drug vs placebo treated patients) for review by the DSMB+ at the end of each 67 patient randomized group. Thus, the study team (and the primary study statistician) will thus remain blinded to patient treatment assignment throughout the course of the study. Due to a clerical error by the Investigational Drug Services that prepares our drug/placebo doses, 69 patients were randomized to the first patient cohort rather than 67. Additionally, because enrollment happens at consent, and not all patients that consent will be randomized, we will keep enrolling patients until we reach 67 consented and randomized patients in each of the last two cohorts.

Assuming that we continue with all three dose groups, at study completion we will have ≥ 117 total CN-105 treated patients and ≥ 39 placebo-treated patients. Given the aforementioned expected grade II or higher AE rates in placebo-treated patients, at completion we will have $>80\%$ power (with $\alpha=0.05$) in a two- sample two-sided unpooled variance chi-square test to detect an absolute difference of 14.8% between grade II or higher AE rates seen in placebo vs CN-105 treated patients. We will also track the rates of other grade II or higher AEs recorded by the patient’s surgical team in the medical record; at study completion we will use 2 sided t tests to compare the rates of any other grade II or higher AEs between placebo vs CN-105 treated patients.

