10.2 Sample Size

We planned to enroll up to 250 patients total in this phase 2 escalating dose study, to obtain three successive groups of 67 randomized patients each. *Because enrollment happens at consent, and not all patients that consent will be randomized, we will keep enrolling patients until we reach 67 consented and randomized patients in each cohort.* In each group of 67 patients, 50 will receive a given dose of CN-105 and 17 will receive placebo. In our recent MADCO-PC study, ~80% of patients returned for the 6 week assessment. Thus, enrolling 67 patients in each group ensures ≥ 52 patients (i.e. 39 CN-105-treated; 13 placebo-treated) will complete the 3 month postop assessment. Due to a clerical error by the Investigational Drug Services that prepares our drug/placebo doses, 69 patients were randomized to the first patient cohort rather than 67. There will be no baseline preoperative cognitive status inclusion/exclusion criteria. Our prior work suggests ~15% of Duke orthopedic surgery patients over age 60 have MCI, ~5% have dementia, and ~80% are cognitively normal. All primary analyses here will be performed on patients grouped together (independent of baseline cognitive status); exploratory analyses will examine effects stratified by baseline cognitive strata, dose level, and by APOE4 carrier status.

Given the aforementioned expected 5% AE rates in placebo-treated patients, at completion we will have >80% power (with $\alpha=0.05$) in a two-sample two-sided unpooled variance chi-square test to detect an absolute difference of 14.8% between grade II or higher AE rates seen in placebo vs CN-105 treated patients (pooling the three dose levels of CN-105 together). We will also track the rates of other grade II or higher AEs recorded by the patient's surgical team in the medical record; at study completion we will use 2-sided t tests to compare the rates of any other grade II or higher AEs between placebo vs CN-105 treated patients.

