10.3 Measures to Minimize Bias

10.3.1 Enrollment/Randomization/Masking Procedures

Participants will be randomized to receive either CN-105 or placebo after they consent to participate in the trial, within 1 week prior to their index surgery. Participants will be enrolled in 1 of 3 dose cohorts (see [Table 1](#)) of 67 subjects each. An independent statistician will prepare dose stratified mixed block size randomization lists in a 3 to 1 ratio to achieve the desired distribution of drug and placebo. In each block of 67 trial participants, 50 will receive a given dose of CN-105 and 17 will receive placebo, in a double-blind fashion. CN-105 will be dissolved in normal saline, and either it or normal saline placebo will be administered as an IV drip over 15-30 minutes. Due to a clerical error by the Investigational Drug Services that prepares our drug/placebo doses, 69 patients were randomized to the first patient cohort rather than 67. Additionally, *because enrollment happens at consent, and not all patients that consent will be randomized, we will keep enrolling patients until we reach 67 consented and randomized patients in each of the last two cohorts.*

CN-105 and placebo will be prepared in identical bags labelled simply with the trial participant's number (1–203) to keep all trial staff and clinicians blinded to randomization. Only the

MARBLE Study – Protocol Version 7**PI: [name], PhD**

investigational pharmacist will have the randomization list that explains which drug (CN-105 or placebo) each participant is to receive and what dose of CN-105 or placebo will be administered every 6 hours (+/- 90 minutes) starting within 1 h before the scheduled or actual start of anesthesia/surgery and continuing until the end of postoperative day 3 (or when the participant is discharged home, whichever comes first), up to a maximum of 13 doses. Each case start time will be defined by the study team as either the start of the surgery/procedure or the start of anesthesia. In order to minimize bias, investigators conducting the laboratory assays on the CSF and blood samples will be blinded to trial group assignment during the course of the trial.

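### The t tests planned for rates of other grade II or higher AEs leave the variance form unstated; the unequal-variance form would inflate false positives at event rates of roughly 2–6%

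*Combined protocol and SAP*

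**What the plan says.** Section 10.1.2 handles adverse events in two steps. The grade II or higher AE rate is assigned a "two-sided unpooled variance chi-square test to detect an absolute difference of 14.8" percentage points, with more than 80% power at alpha 0.05. For other grade II or higher AEs recorded by the surgical team, the next sentence says that "at study completion we will use 2 sided t tests to compare the rates of any other grade II or higher AEs" in the two groups. Section 10.2 repeats this: tests are used "to compare the rates of any other grade II or higher AEs between placebo vs CN-105 treated patients".

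Neither section says whether the t test pools the variances, whether the data are patients with an event or event counts, or what alpha applies. Section 10.1.1 leaves SAS, SPSS and R open. Fisher's exact test is mentioned only for dichotomous POCD in section 10.1.3.

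On numbers, section 10.1.2 says that "at study completion we will have ≥ 117 total CN-105 treated patients and ≥ 39 placebo-treated patients". Section 10.3.1 describes "randomization lists in a 3 to 1 ratio", and section 10.2 says "In each group of 67 patients, 50 will receive a given dose of CN-105 and 17 will receive placebo".

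**The concern.** An individual AE is a yes/no outcome and usually uncommon, and the placebo group is a quarter of the trial. If no placebo patient has the event, the estimated placebo variance is zero. A test that keeps the two variances separate then treats the placebo rate as known exactly, and a few events on drug are enough for significance. A pooled variance avoids this.

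The same data can therefore be a significant safety signal or nothing, depending on an option that the plan does not fix. The comparison would be repeated for each AE type, in a trial whose primary objective is safety, and nearly all the errors of the unequal-variance form count against CN-105.

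**Working it through.** **Inputs.** 117 CN-105 and 39 placebo patients (section 10.1.2); 3 × 50 = 150 and 3 × 17 = 51 as planned at randomization (section 10.2). Nominal two-sided alpha 0.05, stated for the chi-square and assumed for the t tests. The rate of each other AE is not given, so I take the same true rate in both arms, over 0.5% to 30%.

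**The plan's own figure.** For 5% versus 19.8% with 39 and 117 patients, the unpooled standard error is √(0.05 × 0.95/39 + 0.198 × 0.802/117) = 0.0507. Then 0.148/0.0507 − 1.96 = 0.96, a power of 83.1%. Exact enumeration of the two binomials gives 80.1%. The claim of more than 80% power reproduces.

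**One table by hand: 0/39 placebo, 4/117 CN-105.**
- Drug proportion: 4/117 = 0.0342. Sample variance: 0.0342 × 0.9658 × 117/116 = 0.0333. Placebo variance: 0.
- Welch: SE = √(0.0333/117) = 0.0169, t = 0.0342/0.0169 = 2.03 on 116 df, p = 0.045.
- Student: pooled variance = 116 × 0.0333/154 = 0.0251, SE = √(0.0251 × (1/39 + 1/117)) = 0.0293, t = 1.17, p = 0.24.
- Fisher: p = 0.57.

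With no placebo events, Welch therefore needs 4 drug events for significance, Student 11 and Fisher 12.

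**How often this happens by chance.** At a true rate of 3% in both arms, P(0 of 39) = 0.97^39 = 0.305 and P(at least 4 of 117) = 0.467. Their product is 14.2%, which is nearly all of the Welch error at that rate.

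**Exact type I error (%).** This sums the binomial probabilities of every outcome pair with p < 0.05, counting tables with no events as non-significant.

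| Test, patients | 1% rate | 2% | 3% | 5% | 10% | Maximum |
|---|---|---|---|---|---|---|
| Welch, 117 vs 39 | 2.1 | 9.5 | 14.4 | 12.2 | 6.8 | 14.9 (at 3.5%) |
| Student, 117 vs 39 | 2.1 | 3.1 | 3.4 | 4.0 | 4.9 | 5.0 |
| Pooled Pearson, 117 vs 39 | 2.1 | 3.1 | 3.4 | 4.0 | 4.9 | 5.1 |
| Fisher, 117 vs 39 | 0.5 | 1.6 | 2.3 | 2.7 | 3.6 | 4.0 |
| Welch, 150 vs 51 | 3.9 | 12.8 | 14.4 | 9.0 | 6.2 | 14.6 (at 2.7%) |
| Student, 150 vs 51 | 2.6 | 3.5 | 3.9 | 4.7 | 4.5 | 5.0 |

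At 117 versus 39 and a 5% rate, 11.8 of the 12.2 Welch points are false findings that the drug is worse. Welch exceeds 10% only for true rates of about 2.1% to 5.9% (1.7% to 4.5% at 150 versus 51).

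**Event counts instead of patients.** Simulated Poisson counts with mean 0.05 per patient, 117 versus 39, give Welch 12.2% and Student 3.8%.

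**The unpooled-variance chi-square.** At 117 versus 39 it gives 12.5% at a 5% rate, with a maximum of 15.1%. By the same enumeration, power for 5% versus 19.8% is 63.4% with the pooled Pearson test and 62.1% with Fisher's.

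**The case against.** A reader might infer that t tests as such run at two to three times 5% on sparse 3:1 data. The documents do not support that. They name a t test, not the Welch form, and the ordinary pooled version holds its level at every rate checked. This objection stands, and it limits the point to an unspecified option. It does not remove it: the sentence just before the t tests specifies unpooled variance for the same kind of data, so an analyst following that convention would choose Welch.

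A reader might also take the plan's 5% as the rate of an individual AE. Section 10.1.2 gives it for moderate and for severe adverse events as whole categories. Below about 1% Welch is conservative, and at 10% the excess is small.

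The 117 and 39 derive from expected six-week completers. Section 5.4.2 specifies intention to treat for the primary analyses and section 8.3 collects AEs from the first dose, so AE denominators may be nearer 150 and 51. There Welch at a 5% rate is 9.0%, or 1.8 times nominal, though still 14.4% at 3%.

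Finally, these are supporting comparisons at study completion. They are not the main grade II or higher test, and the documents do not tie them to DSMB review or halting, so no effect on those decisions should be inferred.

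**Conclusion.** The point holds in a limited form. The plan applies a t test to binary AE rates without fixing the variance form, and the error rate depends on that choice: at most about 5% with Student, up to 14.9% with Welch at 117 versus 39. The larger figure requires three things: that Welch is chosen, that individual AEs occur at roughly 2–6% (an assumption), and that 5% is the intended level (inferred from the chi-square statement). The cause is separate variances with few events and 3:1 groups, not the t distribution. The unpooled-variance chi-square that the plan does name for grade II or higher AEs therefore has the same weakness at those rates, and there the unpooled form is explicit.

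**What to change.** In sections 10.1.2 and 10.2, replace the t tests by Fisher's exact test, or the pooled Pearson chi-square, on patients with at least one event. State the alpha, and report each risk difference with a score-based 95% CI. Do not substitute the plan's unpooled-variance chi-square.

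Make the same change for the grade II or higher AE comparison and restate its power. For the plan's own scenario at 117 versus 39, the more than 80% becomes about 63% (Pearson) or 62% (Fisher).

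The cost is a few sentences of text, with no change to conduct. Fisher's test is somewhat conservative, and with no placebo events it needs 12 drug events at 117 versus 39, so the intervals should carry the interpretation for rare AEs.

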3.2 Secondary Objectives

Secondary objectives include the following:

- To determine whether CN-105 blocks postoperative neuroinflammation as measured by changes in levels of the following cytokines in the CSF: IL-6, IL-8, MCP-1, and G-CSF.
- To determine whether CN-105 blocks or reduces the risk (or severity) of CCI index change between CN-105 and placebo groups.
- To determine whether participants who receive CN-105 have lower postoperative delirium rates and severity than those who receive placebo.
- To determine whether it is feasible to administer 90% of study doses within the required time window (every 6 hours +/- 90 minutes).

Additional exploratory objectives include:

- To determine whether CN-105 has effects on serum chemistries or blood counts.
- To describe the relationship between anesthetic exposure (both duration, average hourly exposure, total exposure) and CSF inflammatory cytokine changes and demographics (age, sex, and race).
- To describe the relationship between CSF changes in AD and inflammatory biomarkers, anesthetic exposure, and serum markers of metabolic and/or inflammatory status.
- To describe the relationship between anesthetic exposure, CSF and serum biomarker changes, and intraoperative changes in 32-channel (whole head) EEG parameters.
- To determine whether CN-105 blocks the increase in CSF tau levels from before to 24 hours after anesthesia and surgery and whether it modulates changes in CSF phospho-tau and amyloid beta levels from before to 24 hours after anesthesia and surgery.
- To determine whether participants who receive CN-105 (vs placebo) have improved QOL scores 6 weeks after surgery.
- To determine whether participants who receive CN-105 (vs placebo) have reduced abnormalities in intraoperative EEG spectral power patterns.
- To determine if the other primary and secondary outcomes differ among patients who carry the ApoE4 allele or other genetic polymorphisms related to inflammation, neuroimmune function, metabolism, brain function, and/or AD.
- Compare physical function (DASI) and mental health (STAI, SCL-90, and CES-D) before and after surgery in patients who receive CN-105 vs placebo.

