Patients may complete a post-op 1 year study visit (+/-2 months) at which time we will collect blood, perform another LP, and administer the same surveys and cognitive testing that were performed at the baseline and 6 week visits, provided that sufficient funds are available per the PI's judgement at that time. If funding become available after some 1 year time point visits have already been missed, we will potentially perform 1 year visits only on the remaining patients who are still within the correct time window. Likewise, in light of uncertainties surrounding cost and funding due to COVID-19, if other financial changes occur that make it impossible to continue 1 year study visits or any other aspect of this protocol, specific patients may be discontinued based on the PI's judgement and discretion.

Trial duration will be up to 72 months total for participant enrollment and completion of all trial activities, with approximately 6-8 weeks duration for each individual participant (and up to 1 year duration for those who have a 1 year follow up performed), assuming an enrollment rate of ~2 patients per week. If the actual enrollment rate is slower than ~2 patients per week, the trial duration will be longer until we reach full enrollment, though the study duration per patient (~6-8 weeks or 1 year for those with 1 year follow up time) will be unchanged.

Surgical patients may participate in the trial more than once if they desire and are having a second surgery after they have already completed all trial procedures (including the 6 week postoperative time point). There are no known added risks to participants from taking part in the trial additional times, beyond the risks discussed in the informed consent form (ICF).

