6.2.4 Duration of Therapy

Study drug will be administered every 6 hours, with the first dose within one hour of planned or actual case start time, and subsequent drug doses will be given every 6 hours thereafter until postoperative day 3 or hospital discharge, whichever occurs first, up to a maximum of 13 doses. Each case start time will be defined by the study team as either the start of the surgery/procedure or the start of anesthesia (or the timed notes in the EMR for induction, intubation, or the start of anesthetic drug administration). If the case gets delayed by more than 6 hr and we've already given the first dose, we will give an additional dose prior to surgery, but under no conditions will the patient be given more than 13 doses total of CN-105

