6.2.5 Tracking of Doses

Since the immediate pre- and post-operative periods are busy and nurses frequently have numerous tasks to perform, it is important to measure how many CN-105 (or placebo) doses are given as ordered to assess feasibility of q6 h dosing. We will track whether each CN-105 (or placebo) dose is given within +/-90 min of the scheduled administration time per nursing records.

We will report the observed rate of doses administered within the required time window and the 95% confidence interval. Each dose will be counted as an independent observation. The total number of doses correctly administered (i.e. within 90 min of the scheduled administration time) divided by the number of prescribed doses will define our dosing feasibility rate. Post-hoc feasibility analysis will be performed both among all study patients (including those receiving placebo), and specifically among CN-105 drug patients only, as well as by dose level to determine if drug dose level affects feasibility.

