Feasibility Analysis: We will report the observed rate of doses administered within the required time window and the 95% confidence interval. Each dose will be counted as an independent observation. The total number of doses correctly administered (i.e. within 90 min of the scheduled administration time) divided by the number of prescribed doses will define our dosing feasibility rate. Post-hoc feasibility analysis will be performed among all patients, as well as specifically in patients receiving the study drug only, and by dose level to determine if the drug itself or drug dose level affects feasibility.

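### The feasibility confidence interval treats up to 13 doses from one patient as independent, so it is too narrow if on-time dosing is positively correlated within a patient

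*Combined protocol and SAP*

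**What the plan says.** Section 3.2 makes it a secondary objective to find out whether it is "feasible to administer 90% of study doses within the required time window", which is every 6 hours with a tolerance of 90 minutes either way. Section 10.1.2 states the analysis: "We will report the observed rate of doses administered within the required time window and the 95% confidence interval". The rate is the number of doses given on time divided by the number prescribed, pooled over patients. The unit of analysis is then fixed: "Each dose will be counted as an independent observation". Section 6.2.5 repeats this rule.

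Dosing runs "until postoperative day 3 or hospital discharge, whichever occurs first, up to a maximum of 13 doses" (section 6.2.4), so the number of doses varies between patients. Section 4.1 adds that "Surgical patients may participate in the trial more than once if they desire". Post-hoc analyses are planned in all patients, in drug-treated patients only, and "by dose level to determine if the drug itself or drug dose level affects feasibility" (section 10.1.2).

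No interval method is named. For this endpoint there is no robust variance, mixed model, patient-level resampling or sensitivity analysis, no assumed ICC, and no rule that ties the interval to 90%.

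**The concern.** Doses given to one patient are repeated observations on that patient. They are likely to share a hospital, a ward and a nursing team. Section 6.2.5 itself explains the interest in feasibility by saying that the perioperative period is busy and "nurses frequently have numerous tasks to perform". Positive correlation of on-time status within a patient is therefore plausible, although the documents do not measure it. Repeat participation adds dependence within a person.

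If the correlation is positive, the effective number of observations is smaller than the number of doses and the interval overstates precision. Two readings are at risk. One is the comparison of the overall rate with 90%, when the observed rate lies within about 1 to 3 points of that benchmark. The other is the comparison between dose levels, where chance differences between groups of about 50 patients could be taken for an effect of dose on feasibility.

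**Working it through.** **The plan's own figures.** The documents give no interval width, dose total or power for feasibility, so there is no result to reproduce. The 13-dose maximum agrees with the schedule: 72 h / 6 h + 1 = 13.

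**Inputs from the documents**
- Patients: "69 patients were randomized to the first patient cohort rather than 67" (section 10.3.1), with 67 in each later cohort, so 69 + 67 + 67 = 203.
- Planned drug-treated patients per dose level: 50 (section 6.2.2, Table 1).
- Rate: 90%, the benchmark.

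**Assumptions**
- Doses per patient m: uniform on 4 to 13. The mean is 8.5, giving 203 × 8.5 ≈ 1,726 doses.
- ICC: 0 to 0.30.

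**Formulas**
- Planned half-width: 1.96 × √(p(1−p)/n) = 1.96 × √(0.9 × 0.1/1,726) = 1.4 points.
- Design effect: DEFF = 1 + (Σm²/Σm − 1) × ICC. For m uniform on 4 to 13 the mean of m² is 80.5, and 80.5/8.5 − 1 = 8.47, so DEFF = 1 + 8.47 × ICC.
- Half-width allowing for clustering: planned half-width × √DEFF.
- Approximate coverage of the planned interval: 2Φ(1.96/√DEFF) − 1.
- Approximate false-positive rate of a 5% chi-square test on doses across three dose levels (2 degrees of freedom): 0.05^(1/DEFF).

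The last two columns are from beta-binomial simulation (10,000 trials per setting). The false-positive column uses three groups of 50 with no true difference.

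| ICC | DEFF | Half-width needed (points) | Coverage of planned CI | False positives, chi-square on doses |
|---|---|---|---|---|
| 0 | 1.00 | 1.4 | 94.7% | 5.0% |
| 0.02 | 1.17 | 1.5 | 92.8% | 7.7% |
| 0.05 | 1.42 | 1.7 | 89.8% | 12.4% |
| 0.10 | 1.85 | 1.9 | 85.1% | 19.5% |
| 0.20 | 2.69 | 2.3 | 76.4% | 33.1% |
| 0.30 | 3.54 | 2.7 | 70.0% | 43.3% |

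The formulas agree with the simulation. At ICC 0.10 they give 2Φ(1.96/√1.85) − 1 ≈ 85% and 0.05^(1/1.85) ≈ 20%. A Wilson interval on doses has coverage within 0.5 points of that shown, so the choice of binomial interval is not the issue.

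**Sensitivity to the number of doses (ICC 0.10)**
- 4 doses for every patient: DEFF = 1 + 3 × 0.10 = 1.3, coverage 91%.
- 13 doses for every patient: DEFF = 1 + 12 × 0.10 = 2.2, coverage 81%.
- Uniform on 1 to 13: simulated coverage 86%.

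**Against the 90% benchmark.** The planned interval excludes 90% and the clustered one does not when the observed rate is:
- 91.3–91.8% or 87.9–88.5% at ICC 0.10;
- 91.3–92.4% or 87.0–88.5% at ICC 0.30.

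**Does clustering repair it?** In the same simulations a patient-clustered ratio interval covered 94.1–94.9%, and 94.6–95.3% on the logit scale. In a single group of 50 the figures were 92.3–94.4% raw and 94.3–95.2% logit. The clustered logit-scale test across dose levels had a false-positive rate of 4.9–6.3%.

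**The case against.** Feasibility is a secondary endpoint reported descriptively. Nothing requires the interval to exclude 90%, and a rate simply read against 90% does not change. At ICC 0.10 the half-width moves by only half a point, and at 0.02 or below the loss is small. All this stands and limits the weight of the point.

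The ICC and the doses-per-patient distribution are assumed. A floor of 4 doses also sits poorly with same-day discharge, which sections 4.1 and 7.1.2 provide for. That stands for the size, but the 1-to-13 range gives nearly the same coverage and the direction of the error does not depend on it.

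The workload remark in section 6.2.5 describes busy times and units, not patients who are consistently late. That is fair: correlation within a patient is an inference. The same argument implies correlation between patients on one unit, which person-level clustering would miss and which need not be small. For illustration, 20 units of about 86 doses with a unit-level ICC of 0.02 would give DEFF = 1 + 85 × 0.02 = 2.7.

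Finally, the plan names no test for the dose-level comparison. Dose levels are also successive cohorts, so dose is confounded with calendar time. Clustering corrects the error rate of that comparison but not its confounding.

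**Conclusion.** The concern holds. The independence rule is stated explicitly, twice, and nothing elsewhere offsets it. Under any positive within-patient correlation the interval is too narrow. That direction is certain; the size is not, because the documents give no ICC. Under the assumptions above, coverage falls from 95% to about 93% at ICC 0.02, 85% at 0.10 and 70% at 0.30.

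The practical effect on the overall rate is confined to results close to 90%. The dose-level comparison is more exposed, provided it carries the rule over: about one null comparison in five would be significant at ICC 0.10. The definition of the rate, the primary safety endpoint and the halting rules are not touched. This should be corrected, but it does not threaten the trial's main conclusion.

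**What to change.** In sections 6.2.5 and 10.1.2, replace the independence sentence with wording such as: *The 95% CI will be computed with the person as the cluster (all enrolments of a repeat participant in one cluster), using a cluster-robust ratio estimator on the logit scale.* A person-level bootstrap is an acceptable alternative, but the plan should name one method. The logit scale is preferred because it holds coverage better in groups of 50.

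Keep the rate as on-time doses over prescribed doses. GEE with working independence and robust variance gives the same estimate. Exchangeable GEE should be avoided, because it reweights patients and changes the defined rate. Suppose half the patients have 4 doses at 95% and half have 13 at 88%. The defined rate is (4 × 0.95 + 13 × 0.88)/17 = 89.6%. Exchangeable weights at ICC 0.10 are 4/1.3 = 3.08 and 13/2.2 = 5.91, which give 90.4%.

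Use the same clustering for the drug-only and dose-level analyses, report the estimated ICC, and note that dose level coincides with enrolment period. Make the change before the unblinding described in section 10.3.2.

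The cost is one sentence in two sections and a few lines of code, with no new data. At ICC 0 the interval is practically unchanged (1.41 points either way); otherwise it widens as shown. Correlation between patients on the same unit would remain unaddressed and should be stated as a limitation.
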